#### Statistical evaluation

The statistical analyses will be done in cooperation with a statistician. The analyses will compare scores in each evaluation point between evaluation points between the intervention and the control group. Outcomes will be assessed at weeks 8 and 24 of the study. Analyses will be conducted on the full sample (intent to treat analysis).

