## **Primary Endpoint**

- Change in IBS symptoms based on the IBS symptom severity score (SSS) score at week 8 compared to baseline

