**Table 1: Collection of Questionnaire Data**

Questionnaire	Week 0 (Day 0)	Week 4 (Day 28)	Week 8 (Day 56)	Week 24 (Day 168)
Demographic information	x			
Prior IBS Medication Usage	x			
Current medication usage	x	x	x	
IBS-SSS	x	x	x	x
PSQ	x			x
WSAS	x			x
SGA	x			x
HADS	x		x	x
WPAI	x		x	x

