### Power

We estimate that with an initial sample size of 22 participants per intervention group and 22 per control group, we will have 80% power (alpha 0.05) to detect the minimal clinically important difference on the IBS-SSS. We expect a minimum reduction in score

of 50 points, which is considered to be a considerable improvement.ix In order to account for patient withdrawal from the trial we aim to enroll 30 patients in each study group.

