#### Study completion

Patients who have completed all of the IBS-SSS at weeks 0, 4, 8, and 24 will be considered completers of the study.

SCHEDULE OF ASSESSMENTS				
Protocol Activity	Week 0 Day 0*	Week 4 Day 28*	Week 8 Day 56*	Week 24 Day 168*
Informed consent	X			
Inclusion/Exclusion Screening	X			
Randomization	X			
Zemedy onboarding (if CBT)	X			
Physician Visit	X		X	X
Demographic Information	X			
Current Medications	X	X	X	
Fecal Sampling/Microbiome (opt-in)	X		X	X**
IBS-SSS	X	X	X	X
PSQ	X			X
WSAS	X			X
SGA	X			X
HADS	X		X	X
WPAI	X		X	X
Compensation			X	X

\*The study window is six days, + / - 3 days from the noted day.

\*\*Sample collection contingent on PI judgment.

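### The week-8 IBS-SSS comparison names no model or covariate; adjusting it for the baseline score already scheduled would be a free gain in precision

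*Combined protocol and SAP*

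**What the plan says.** The section Statistical evaluation is the whole analysis plan. Its operative sentence is "The analyses will compare scores in each evaluation point between evaluation points between the intervention and the control group". It adds that "Outcomes will be assessed at weeks 8 and 24 of the study" and that "Analyses will be conducted on the full sample (intent to treat analysis"). It names no test, model, covariate or missing-data method, and no other section supplies one.

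The Primary Endpoint section defines the outcome as "Change in IBS symptoms based on the IBS symptom severity score (SSS) score at week 8 compared to baseline".

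The table headed "Table 1: Collection of Questionnaire Data" and the Schedule of Assessments both place IBS-SSS at weeks 0, 4, 8 and 24. PSQ and WSAS are collected at weeks 0 and 24, and HADS at weeks 0, 8 and 24.

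The Power section claims 80% power at alpha 0.05 with an "initial sample size of 22 participants per intervention group and 22 per control group", and cites a 50-point reduction. It then states: "In order to account for patient withdrawal from the trial we aim to enroll 30 patients in each study group".

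The section Study completion adds a definition: "Patients who have completed all of the IBS-SSS at weeks 0, 4, 8, and 24 will be considered completers of the study". No analysis refers to that group.

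**The concern.** The analysis sentence is garbled and speaks only of scores. It leaves three analyses open: raw week-8 scores, change from baseline, or week-8 scores adjusted for baseline. All three estimate the same arm difference under randomisation with complete data, but their precision differs. With about 22 evaluable patients per arm, that difference in precision is not trivial. The baseline value needed for the most precise of the three is already in the schedule.

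A smaller point sits beside it. The plan expects withdrawal and promises the full sample, but does not say how a randomised patient without a week-8 score enters the result. Enrolling extra patients protects the number analysed. It does not protect against bias if those who leave differ from those who stay.

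**Working it through.** **Inputs from the document.** 22 per arm, 80% power, alpha 0.05, 50 points, 30 enrolled per arm.

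**Assumptions not in the document.** A two-sided test; equal variance s² at baseline and week 8; correlation r between the two of 0.3, 0.5 or 0.7; 50 points read as a difference between arms.

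**1. The plan's own figure.** No SD is given, so the 80% can only be solved backwards. With the noncentral t on 42 df, 22 per arm gives 80% power at a standardised difference d = 0.865, which is a noncentrality of 0.865 × √(22/2) = 2.868. For 50 points the SD would have to be 50/0.865 = 57.8. The normal approximation gives 50/[(1.960 + 0.842) × √(2/22)] = 59.2. The document does not say whether such an SD would belong to raw scores or to changes.

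**2. Variances of the three analyses.**
- Raw week-8 score: s²
- Change score: 2(1 − r)s²
- ANCOVA: (1 − r²)s²

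Hence ANCOVA/change = (1 + r)/2 and ANCOVA/raw = 1 − r².

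| r | ANCOVA / change | ANCOVA / raw |
|---|---|---|
| 0.3 | 0.65 | 0.91 |
| 0.5 | 0.75 | 0.75 |
| 0.7 | 0.85 | 0.51 |

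**3. Power of ANCOVA at 22 per arm.** Divide the noncentrality 2.868 by the square root of the ratio and use 41 df, one fewer for the covariate.

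| r | If the change-score test has 80% | If the raw-score test has 80% |
|---|---|---|
| 0.3 | 2.868/√0.65 = 3.557, 93.5% | 2.868/√0.91 = 3.006, 83.5% |
| 0.5 | 2.868/√0.75 = 3.311, 89.8% | 2.868/√0.75 = 3.311, 89.8% |
| 0.7 | 2.868/√0.85 = 3.110, 85.9% | 2.868/√0.51 = 4.016, 97.5% |

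The formula ignores chance baseline imbalance. A simulation of plain ANCOVA with 22 per arm, under the raw-score calibration, gave 82.5%, 89.2% and 97.1%, with type I error of about 5%. At r = 0 the formula loses less than 0.1 percentage point against the raw-score test.

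**4. Cost of leaving the sentence open.** If the 80% was worked out for raw scores and r = 0.3, a change-score test has 66%. If it was worked out for change and r = 0.7, a raw-score test has 58%. ANCOVA gives the same arm difference whether the outcome is entered as score or as change, so the choice disappears.

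**5. Missing week-8 scores (illustration).** The enrolment margin is 30 − 22 = 8 per arm, or 8/30 = 26.7%. This is not a stated withdrawal rate. If 8 of 30 app-arm patients had no week-8 score and their true values were 50 points worse than assumed, the estimate would move by 50 × 8/30 = 13.3 points. A 50-point effect would then become 50 − 13.3 = 36.7.

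**The case against.** The strongest reply is that baseline is not ignored. The Primary Endpoint section already defines change from baseline, and the analysis sentence, with its wording about evaluation points, can be read as comparing change between arms. That stands. A reader might infer that the two sections contradict each other or that an unadjusted analysis would be invalid, but the document supports neither inference. The wording is ambiguous, and under randomisation with complete data the unadjusted comparison is valid.

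It also follows that, if the endpoint definition governs, the relevant gain is the one over the change score, from 80% to between 85.9% and 93.5%. The wider range depends on calibrating the 80% to raw scores. All these figures rest on an SD and a correlation that the document does not give. The absence of an SD makes the 80% uncheckable; it does not show it to be wrong.

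On missing data, a reader might infer that the completers will replace the full sample. The text does not say so. Statistical evaluation fixes the full sample by assigned arm, and the completer definition reads as a status label. What remains is missing detail: no rule for an absent week-8 score, and no stated role for the completers.

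A repeated-measures model over all four visits could also be proposed. Simulation of a three-visit approximation gave almost the same power as plain ANCOVA on 22 per arm, so the added machinery is hard to justify here.

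**Conclusion.** This is a free improvement, not a flaw that invalidates the trial. Naming baseline-adjusted ANCOVA would cut the variance to 65% to 85% of the change-score variance for correlations of 0.3 to 0.7, and it would settle which quantity is tested. The size rests on equal variances and on that assumed range of correlation. The power figures rest in addition on taking the stated 80% as true for one of the two unadjusted tests. The missing-data and completer points are secondary gaps in detail. The 13.3-point shift shows how large the effect could be under one assumption and predicts nothing about actual withdrawal.

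**What to change.** Replace the comparison sentence in Statistical evaluation with:

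> The primary analysis compares week-8 IBS-SSS between arms by ANCOVA adjusted for baseline IBS-SSS, with 95% CI, by assigned arm. The adjusted arm difference is the same for the score and for change from baseline. Week-24 IBS-SSS, PSQ and WSAS, and week-8 and week-24 HADS, are analysed in the same way, each with its own baseline value.

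As a secondary, low-cost addition:

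> Missing week-8 IBS-SSS scores are multiply imputed from baseline, week 4 and arm. A sensitivity analysis worsens the imputed app-arm scores over a stated range (for example 0 to 50 points). The set of completers is descriptive or supportive only.

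The shift range is a probe of the missing-at-random assumption, not a correction to a known value. WPAI and SGA are outside this proposal.

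The cost is one degree of freedom, some wording and slightly more analysis work. No new data, visits or patients are needed.

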#### Roles and resourcing of the study

Principal Investigators (PI) [name] and [name] will be responsible for the oversight of the study, and are responsible for approving all candidates to become study participants. Both PIs are responsible for making sure that the study is conducted in an ethically sound manner as well as is safe for the participating patients.

#### Ethical considerations

Completing the questionnaires, taking part in the digital program, being in the control group, and all other time spent related to the study are additional efforts to the treatment the subjects would otherwise receive. In our view, the burden of taking part in the study is moderate for the participant. They are advised to contact the study PIs at any point if any questions or adverse effects arise. An interim safety analysis will be performed under consultation with the team gastroenterology psychologist.

All participating individuals will sign an informed consent to take part in the study and they will have an appropriate amount of time to familiarize themselves with the study before making the decision to participate. The study and all related activities such as extra phone consultation are completely free of charge for the participants. The results are confidential and will be kept in a safe and encrypted storage within the Redcap system (more information in the Data collection chapter). The statistical analyses will be performed without any personal identification information by assigning anonymous identification codes to all subjects.

#### Data collection

All captured study data and personal information (such as the participant's name, phone number, address and any free-text entered by the participants) will be stored in the Redcap system. It will be blinded from any analysis or data extraction. Patient identifiers and contact information will only be available to the study investigator, study therapist or any support staff working directly with patients that need this information for logistical or patient support purposes. All data used for reporting or publications will be anonymized.

All Zemedy related data (such as exercises related data or patient nick name) will be stored in the Zemedy application system. The Zemedy application system is not collecting or maintaining personal identifiable information and is thus not a patient registry.

Data to be collected include age, gender, comorbidities, medications (prescription and over the counter) and diagnostic testing performed (bloodwork, procedures)

#### Quality assurance

All data captured in the study will be in electronic format and stored in the Redcap system and/or in the Zemedy Program system. All patient identifiable information and data will be stored in the Redcap system which is a safe server-system with appropriate data protection, privacy and information security features.

#### Adverse experience reporting

Any adverse experiences with the Zemedy Program will be monitored during the study by the study investigators. PIs will consult with the team's Gastroenterology psychologist.

### **Human subjects**

#### Ethical committee review and informed consent

This protocol and the informed consent document and any subsequent modifications will be reviewed and approved by the IRB committee responsible for oversight of the study. A consent form will be obtained from the subject. The consent form will describe the purpose of the study, the procedures to be followed, and the risks and benefits of participation. A copy of the consent form will be given to the subject, or legal guardian, and this fact will be documented in the subject's record.

#### Confidentiality

All captured data will be identified only by the Study Identification Number to maintain subject confidentiality. All captured data will be encrypted in the database. Clinical information will not be released without written permission of the subject, except as necessary for monitoring by IRB, the sponsor, or the sponsor's designee.

#### Study modification/discontinuation

The study may be modified or discontinued at any time by the IRB, the sponsor, as part of their duties to ensure that research subjects are protected.

#### Study completion

Patients who have completed all of the IBS-SSS at weeks 0, 4, 8, and 24 will be considered completers of the study.

SCHEDULE OF ASSESSMENTS				
Protocol Activity	Week 0 Day 0*	Week 4 Day 28*	Week 8 Day 56*	Week 24 Day 168*
Informed consent	X			
Inclusion/Exclusion Screening	X			
Randomization	X			
Zemedy onboarding (if CBT)	X			
Physician Visit	X		X	X
Demographic Information	X			
Current Medications	X	X	X	
Fecal Sampling/Microbiome (opt-in)	X		X	X**
IBS-SSS	X	X	X	X
PSQ	X			X
WSAS	X			X
SGA	X			X
HADS	X		X	X
WPAI	X		X	X
Compensation			X	X

\*The study window is six days, + / - 3 days from the noted day.

\*\*Sample collection contingent on PI judgment.

## Amendment Summary

### Amendment 1 (Protocol Version 2)

- Addition of [name] as sub-investigator
- Addition of fecal sampling (weeks 0, 8, and possibly 24) and microbiome analysis
  - Optional; patient must be willing and able to provide stool sample
  - Stool kits will be given or mailed after consent
- Adjustment to exclusion criteria
  - Current or past diagnosis of a major mental illness such as schizophrenia, bipolar disorder, personality disorder or substance abuse
  - Prisoners or other detained individuals.
  - Adults unable to consent
  - [Pregnant] "people"

### Amendment 2 (Protocol Version 3)

- Correction of scheduling typos in secondary endpoint section
- Addition of HADS assessment to Week 8 visit in the schedule of assessments
- Adjustment to HADS abnormal threshold ( >15 instead of >11)
- Adjustment to exclusion criteria
  - Removal of
    - Severe anxiety or depression assessed by the HADS scale
  - Addition of
    - Psychiatric hospitalization within 10 years
    - Active (within the past 3 months) suicidal ideation
- Addition of safety assessment for suicidal ideation to Physician's Visit
- Addition of gastroenterology psychologist consult
  - for adverse events
  - for interim safety analysis

